5.3 Concomitant Interventions

5.3.1 For Both Thrombolysis and Non-Thrombolysis Subjects

According to the principle of the ALIAS Trial as a large simple trial of ALB compared to placebo over and above the best standard of care, few restrictions on concomitant care are made. However, one exception is that fluid management procedures and diuretic use mandates must be followed.

Mandatory

Fluid Management: Subjects shall receive no additional intravenous fluid during infusion of study drug with the exception of standard IV thrombolysis. IV thrombolysis should be given, if appropriate, through a dedicated IV catheter. After completion of study drug infusion (2 hour +/- 15 min.), the subject may receive no more than 75 cc/h of IV fluid for the next 46 hours. Normal saline (0.9% NS) is the preferred IV solution since glucose may promote worsening of ischemic brain injury. The total intravenous fluid received in the first 48 hours of care should not exceed 4200ml (~600 ml study drug + 75ml/h 0.9% NS + 90 ml thrombolysis = 4140 ml). Note that obese or large subjects >100 kg may receive 4290 ml according to the same formula. Strict ins (IV fluids only) and outs should be measured for the first 48 hours of a subject's care. There may be situations where additional fluid

is required because of a subject's condition (e.g., shock or hemorrhage). Any exceptions made to the fluid administration mandate must be documented in the CRF.

Diuretics: In general, stroke patients should be treated aiming for euvolemia. One potential complication of ALB infusion is volume overload with subsequent pulmonary congestion. Diuretics may be used in the acute phase to promote diuresis to allow subjects to better compensate for an episode of pulmonary congestion. Loop diuretics such as furosemide are preferred because they act quickly and can be administered intravenously. A single dose of furosemide, 20 mg IV, (or an equivalent loop diuretic such as ethacrynic acid) should be administered as a routine standard-of-care between 12 and 24 hours after the start of study drug administration. If the treating physician chooses not follow this treatment guideline, the reason for withholding diuretic must be documented in the case report form. From the time of treatment through 24 hours, all subjects are evaluated for evidence of respiratory compromise due to congestive heart failure.

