Recommended Best Care: Over the first 7 days of in-patient care, subjects' cardio-respiratory status should be reviewed with particular care. It is over this time period that ALB will redistribute in the body and exert an oncotic effect. Close continued attention to the fluid balance, and cardiac status is required. Treating neurologists should have a low threshold to promote diuresis during the acute hospital stay.

Antiplatelet/anticoagulant therapy: Antiplatelet therapy should be administered to all subjects within 48 hours of their stroke. Aspirin (ASA, acetylsalicylic acid), 81-325 mg daily (low dose) is the preferred drug. Subjects who are naïve to ASA may be loaded with 160 mg ASA on the first day of their dosing. Subjects who receive IV thrombolysis should not be treated with ASA until 24 hours after thrombolysis therapy, and after a 24-hour neuroimaging procedure shows no evidence of intracranial hemorrhage. Subjects who are hypersensitive to ASA may receive clopidogrel. Combined ASA and dipyridamole (Aggrenox™) is an acceptable alternative to ASA or clopidogrel. Ticlopidine is not an acceptable alternative to ASA because of known hematologic toxicity.

Anticoagulation: Anticoagulation with heparin is discouraged. There is no general evidence that heparin is useful in the acute management of stroke subjects for any stroke type. Low-dose subcutaneous unfractionated heparin or low molecular weight heparin may be given after 24 hours, to prevent deep venous thrombosis/pulmonary thromboembolism.

Blood pressure reduction: Blood pressure may be treated according to the local standards of the clinical sites and the standards for thrombolysis treatment. According to the principle of this Trial, whose goal is to assess ALB therapy over and above standard-of-care, no restrictions on blood pressure are in place prior to ALB/placebo therapy. Blood pressure and blood pressure treatments in the acute phase must be recorded.

Glucose-lowering therapy (insulin): Currently, there are no completed controlled trials to suggest that lowering glucose in the acute phase results in improvements in clinical outcome among acute stroke subjects. However, subjects with myocardial infarction and critically ill subjects may benefit from aggressive glucose control [77]. Elevated glucose is associated with a higher rate of symptomatic intracranial hemorrhage after thrombolysis therapy [27,104]. Risk factors for

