Adverse events are further graded as mild, moderate, severe, life-threatening, or fatal. Adverse events that are non-serious must be followed through the 3-month follow up visit. Only serious adverse events are reported beyond the 3-month follow up visit.

An **unexpected adverse event** is any event for which the specificity or severity is not consistent with the current investigator brochure; or, an adverse event for an individual subject that may be adjudicated to be “unexpected” in view of the severity, the timing, and/or the medical context in which it occurs. The study site PI should take all factors carefully into account in deciding whether he/she believes that the event is expected or unexpected.

A **Serious Adverse Event (SAE)** is one that results in any of the following outcomes:

- death due to any cause;
- a life-threatening adverse experience (i.e., the subject was at immediate risk of death from the event as it occurred);
- in-patient hospitalization or prolongation of existing hospitalization. (Hospitalizations scheduled before enrollment for an elective procedure or treatment of a pre-existing condition that has not worsened during participation in the study is not considered a serious adverse event);
- a persistent or significant disability/incapacity (i.e., a substantial disruption of one’s ability to conduct normal life functions);
- a congenital anomaly/birth defect;
- an important medical event that may not result in death, be life-threatening, or require hospitalization, but may jeopardize the subject and may require medical or surgical intervention to prevent one of the outcomes listed in this definition. Any new diagnosis of cancer (made after study enrollment) is considered an important medical event.

For the ALIAS Trial, **severe, or life-threatening** pulmonary edema or CHF (as defined in Section 8.2) occurring within 48 (\pm 6) hours of randomization is considered a SAE. All serious adverse events must be followed for the duration of the 12-month trial or until resolution, whichever comes first.

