8.2 Formal Definitions of Selected Adverse Events

Acute Congestive Left Heart Failure/Pulmonary Edema. Acute CHF is defined as pulmonary edema occurring within 48 (\pm 6) hours of randomization. Pulmonary edema is characterized by all of the following: (a) supplemental oxygen requirement or an increase in oxygen requirement with associated fall in SaO₂; (b) elevated respiratory rate and tachycardia; (c) physical examination evidence of pulmonary congestion including elevated jugular venous pressure, presence of hepatjugular reflux, pulmonary auscultatory rales or wheezing.

Although a CXR is not required for diagnosis, if one is done and shows radiological evidence of pulmonary edema it will support the diagnosis.

Acute CHF/pulmonary edema is further classified as:

- (i) Asymptomatic – the subject requires no additional therapy. Pulmonary congestion may be only shown on CXR in this case.

- (ii) Mild – the subject requires and responds to the single mandated dose of a diuretic and requires supplemental oxygen via nasal prongs only. A single dose of diuretic shall be considered 20mg of intravenous furosemide.
- (iii) Moderate – the subject requires more than the mandatory dose of a diuretic but responds and requires supplemental oxygen via nasal prongs only.
- (iv) Severe – the subject requires treatment with multiple doses of diuretic, supplemental oxygen via face mask, or additional problems arise such as cardiac arrhythmias and cardiac telemetry is required.
- (v) Life-threatening – the subject requires intubation or non-invasive BiPAP/CPAP to manage significant hypoxemia.

Acute coronary syndrome (MI). Elevated cardiac-specific CK (total CK-MB mass), troponin-T, or troponin-I greater than the upper limit of normal (ULN) at the clinical site **plus** clinical symptoms or EKG evidence of myocardial injury (ST deviation ≥ 1 mm in 2 contiguous leads or new/previously undocumented Q waves). [120]

Myocardial injury without acute coronary syndrome -- “enzyme leak”. Elevated cardiac-specific CK (total CK-MB mass), troponin-T, or troponin-I greater than the upper limit of normal (ULN) at the clinical site in the absence of clinical symptoms or EKG evidence of an acute coronary syndrome.

Acute coronary syndrome - unstable angina. Clinical symptoms (chest pain, dyspnea) or EKG evidence (ST depression or T wave inversion) of reduced myocardial flow without a significant elevation in cardiac enzymes. [120,121]

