8.5 Review and Expedited Reporting of Serious Adverse Events

All serious AEs must be reported by the site into the WebDCU™ system within 24 hours of first knowledge of the SAE. Additionally, all current study data for that particular subject must be entered to allow for timely review by the MSMs. Upon entry of a serious AE, WebDCU™ triggers notification of the SAE to the Project Manager. The narrative section of the SAE report is reviewed by an AMM, and if the narrative is satisfactory the SAE is forwarded to the MSMs.

The MSMs conduct independent blinded reviews of all SAEs entered into WebDCU™. Should any medical reviewer need additional subject data to conduct his review, those data may be accessed on the WebDCU™. The MSMs submit their opinions on whether the AE was a) serious, b) unexpected, and c) related to the study drug within 72 hours of notification of the SAE. The MSMs may contact the site for more information or discussion. If two of the three parties involved with the

reporting and/or reviewing of the SAE (i.e., site investigator and either of the MSMs, both MSMs, or all three) believe the AE is serious, study drug-related (possibly, probably or definitely), and unexpected, the SAE is considered to require expedited reporting.

When it is confirmed that an event requires expedited reporting, the Project Manager contacts the site with instructions for completion of a MedWatch form, or other safety reporting forms. An electronic copy of the MedWatch form is sent through the WebDCU™ system and the site staff enters the required information. Following the site's completion of the MedWatch form, or other safety reporting form, SDCC submits the MedWatch form, or other safety reporting forms, to the FDA. SDCC also distributes this information to the DSMB (through the NINDS DSMB Liaison), Health Canada (through the Canadian Coordinating Center), and the clinical site PIs. Each clinical site PI is then responsible for reporting to his/her own IRB/REB.

[figure not shown]

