8.8 Monitoring of Specific Adverse Events

Incidences of the following specific adverse events are monitored by the Trial EC in a blinded manner and by the unblinded Trial personnel and the DSMB by treatment group throughout the study:

- Neurological deterioration as assessed by the investigator of an increase of 4 points or more on the NIHSS anytime within 48 (\pm 6) hours of randomization
- Neurological death from stroke during hospitalization or within 7 days (\pm 6 hours) of randomization, whichever is shorter
- Recurrent stroke within 30 (\pm 7) days of randomization
- Atrial fibrillation within 48 (\pm 6) hours of randomization
- Severe or life threatening pulmonary edema or CHF within 48 (\pm 6) hours of randomization
- Shortness of breath within 48 (\pm 6) hours of randomization
- Symptomatic ICH within 24 (\pm 6) hours of randomization
- Asymptomatic ICH as assessed by the CT scan at 24 (\pm 6) hours
- Death from any cause within 30 (\pm 7) days of randomization
- Death from any cause within 90 (\pm 14) days of randomization

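### Protocol Section 8.2 lets one heart-failure case be both moderate and severe, although severe is the cut for CHF-specific SAE status and for the by-arm CHF count

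*Protocol*

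**What the plan says.** Protocol Section 8.2 defines acute CHF as pulmonary edema within 48 (±6) hours of randomization and gives it five grades. The two at issue are:

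- Moderate (iii): "the subject requires more than the mandatory dose of a diuretic but responds and requires supplemental oxygen via nasal prongs only".
- Severe (iv): "the subject requires treatment with multiple doses of diuretic, supplemental oxygen via face mask, or additional problems arise such as cardiac arrhythmias", the last of these with a need for telemetry.

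The mild grade (ii) fixes the unit: "A single dose of diuretic shall be considered 20mg of intravenous furosemide". Section 5.3.1 gives every subject one such dose, which "should be administered as a routine standard-of-care between 12 and 24 hours after the start of study drug administration". This is the mandated dose that grades (ii) and (iii) refer to.

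Two rules use the grade. Section 8.1 makes an SAE of severe or life-threatening "pulmonary edema or CHF (as defined in Section 8.2) occurring within 48" (±6) hours of randomization. Section 8.8 lists "Severe or life threatening pulmonary edema or CHF within 48" (±6) hours among the events followed by treatment group by the unblinded personnel and the DSMB.

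**The concern.** A scale that drives reporting has to put each case in exactly one grade. Here the moderate grade is bounded by oxygen route and response, while the severe grade opens with a diuretic criterion that carries neither bound. The criteria in the severe grade are joined by *or*, so repeated diuretic dosing appears sufficient by itself. Section 8.2 has no rule for a case that meets two grades.

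The grade decides how the event is handled. A severe case must be entered within 24 hours (8.5), needs a narrative and relationship ratings (8.4), and is followed to resolution or 12 months (8.1). A non-serious moderate case is followed only through the 3-month visit. Review differs too: "The MSMs conduct independent blinded reviews of all SAEs entered into" the study database. The monitors can therefore question a case entered as severe, but would not routinely see the same case entered as moderate. Section 7.1 names volume overload as the main worry with albumin, so this is a safety item that should be counted the same way everywhere.

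**Working it through.** The protocol states no figure on this point, so the check is one of logic. The inputs are the Section 8.2 grades, the 20 mg dose unit (8.2) and the single routine dose (5.3.1).

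Take a subject who meets the Section 8.2 definition of pulmonary edema, responds to diuretic, and has no arrhythmia and no ventilation. Total furosemide includes the mandated 20 mg, so 40 mg is 2 × 20 mg (two doses) and 60 mg is 3 × 20 mg (three doses). Three readings of the severe grade are possible:

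- A: any one criterion suffices, and *multiple* counts all doses.
- B: any one criterion suffices, and *multiple* counts only doses beyond the mandated one.
- C: multiple doses (all counted) are required together with face mask or additional problems.

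| Furosemide, oxygen | A | B | C |
|---|---|---|---|
| 20 mg, prongs | mild | mild | mild |
| 40 mg, prongs | moderate and severe | moderate | moderate |
| 60 mg or more, prongs | moderate and severe | moderate and severe | moderate |
| 20 mg, mask | severe | severe | no grade |
| 40 mg, mask | severe | severe | severe |
| 60 mg or more, mask | severe | severe | severe |

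Under A, counting in whole 20 mg doses, every moderate case also meets severe. Under B the overlap starts one dose later. Under C it disappears, but face-mask oxygen after the mandated dose alone fits no grade, because mild and moderate both require prongs only. No reading gives every row exactly one grade.

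Response does not separate the grades either. Moderate requires a response, but severe does not require its absence. A subject on prongs who fails repeated diuretic is severe under A. Under C that subject has no grade: mild and moderate both need a response, and severe would need a mask or an additional problem.

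Now trace one case: 40 mg in total, responding, on prongs. A site using A enters an SAE and adds one to the 8.8 count. A site using B or C enters a non-serious AE and adds nothing, unless a general SAE criterion is met.

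**The case against.** The strongest reply is that the intention is clear. Moderate stops at prongs with a response; severe moves on to face mask and complications. A reading that nearly empties the moderate grade can hardly have been meant, and under B one further 20 mg dose is simply moderate. This is fair, and the full overlap does depend on reading A. But the text does not state the intended split, *or* makes the diuretic criterion sufficient, and the reading that restores the split opens a gap elsewhere.

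A second reply is that few cases need fall in the overlap. The advice that "Treating neurologists should have a low threshold to promote diuresis during the acute hospital stay" concerns fluid management over the first 7 days, and extra furosemide does not by itself make a case. Section 8.2 also requires an oxygen need with falling saturation, raised respiratory rate with tachycardia, and signs of congestion on examination. This stands: the protocol does not show that the overlap is common.

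A reader might infer that moderate cases are lost to the DSMB. They are not. Non-serious AEs are recorded with severity (8.4), all AEs reach the DSMB in aggregate (8.7), monthly reports give safety data by group code (10.7.3), and shortness of breath within 48 hours is its own item in 8.8. A moderate case can also be an SAE on general grounds, such as prolonged hospitalization. What a moderate grade can cost is expedited entry, monitor review and a place in the 8.8 CHF count.

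**Conclusion.** The point holds as a defect in a stated definition: grades (iii) and (iv) are not mutually exclusive on the literal reading, and the joint reading leaves a gap. SAE capture and the 8.8 CHF count therefore depend on how each site reads Section 8.2. It should be corrected, but it does not threaten the trial's main conclusions.

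Its size cannot be derived. The protocol gives no rates by diuretic dose and oxygen route. A reader might take a rate from Phase I, where 7.1 reports clinical signs of CHF in about 13%, all called mild and managed with at most 2 furosemide doses. That does not carry over. Milligrams per dose and oxygen route are not given, and the Section 8.2 criteria are not shown to have been met. In the top dose tier, 11 of 12 subjects received no furosemide, whereas Part 2 has a routine dose, a fluid cap, cardiac exclusions and an upper age of 83, against a Phase I maximum of 88.

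A reader might also infer a bias between arms or a weakened stopping rule. Neither is supported. Grading is double-blind, and assignment balances arms within and across sites (4.3.3), so differing site readings should not favour an arm. The CHF item has no statistical boundary; the formal safety guideline uses 30-day mortality (10.7.2). Alpha, power and the primary outcome are untouched.

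**What to change.** Rewrite two grades in Section 8.2:

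- Moderate: more than the mandated diuretic dose, with a response, oxygen by nasal prongs only, and no additional problem needing telemetry.
- Severe: face-mask oxygen; or an additional problem, such as arrhythmia, needing telemetry; or failure to respond to repeated diuretic doses, whatever the oxygen route.

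Add that the highest grade met applies, and use the same rule for the 8.8 item. State what repeated means, for example the mandated dose plus at least one more, so that the ambiguity does not return. The non-response criterion matters: if oxygen route and arrhythmia alone marked severe, a subject on prongs who fails repeated diuretic would not be severe.

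With this wording each row of the table has one grade: 20 mg on prongs is mild, 40 mg or more on prongs with a response is moderate, and any face-mask case short of ventilation is severe.

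The cost is a wording change, with cases already graded moderate or severe regraded once. Diuretic use is already collected through 48 hours (6.1); the sponsor should confirm that oxygen route and response are recorded. SAE counts will shift slightly: down where sites counted responders on prongs as severe, and up where they required the severe criteria jointly.

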4.2 Exclusion Criteria

1. Episode/exacerbation of congestive heart failure (CHF) from any cause in the last 6 months. (An episode of congestive heart failure is any heart failure that required a change in medication, diet or hospitalization.)
2. Known valvular heart disease with CHF in the last 6 months.
3. Known (or in the Investigator's judgment) existence of severe aortic stenosis or mitral stenosis
4. Cardiac surgery involving thoracotomy (e.g., coronary artery bypass graft (CABG), valve replacement surgery) in the last 6 months.
5. Acute myocardial infarction in the last 6 months.
6. Signs or symptoms of acute myocardial infarction, including EKG findings, on admission.
7. Elevated serum troponin level on admission > 0.1 mcg/L.
8. Suspicion of aortic dissection on admission.
9. Acute arrhythmia (including any tachy- or bradycardia) *with* hemodynamic instability on admission (systolic blood pressure < 100 mmHg).
10. Findings on physical examination of *any* of the following: (1) jugular venous distention (JVP > 4 cm above the sternal angle); (2) 3rd heart sound; (3) resting tachycardia (heart rate > 100/min) attributable to congestive heart failure; (4) lower extremity pitting edema attributable to congestive heart failure; (5) bilateral rales; and/or (6) if a chest x-ray is performed, definite evidence of pulmonary edema, bilateral pleural effusion, or pulmonary vascular redistribution.
11. Current acute or chronic lung disease requiring supplemental chronic or intermittent oxygen therapy.
12. Historical modified Rankin Scale (mRS) ≥ 2 . Patients who live in a nursing home or who are not fully independent for activities of daily living (toileting, dressing, eating, cooking and preparing meals, etc.) immediately prior to the stroke are not eligible for the trial.
13. Patients with in-patient stroke.
14. Profound dehydration
15. Fever, defined as core body temperature > 38.0°C (100.4°F).
16. Serum creatinine > 2.0 mg/dL or 180 μ mol/L.
17. Severe chronic anemia (hemoglobin < 7.5 g/dL or 75g/L).
18. Evidence of intracranial hemorrhage (intracerebral hematoma, intraventricular hemorrhage, subarachnoid hemorrhage (SAH), epidural hemorrhage, acute *or* chronic subdural hematoma (SDH)) on the baseline CT or MRI scan.
19. History of or known allergy to albumin.
20. History of or known allergy to natural rubber latex.

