6.2.2 Evaluations During Hospitalization Following ALB/Placebo Administration

Vital signs are monitored at a minimum of four times daily (q6h) through Day 7 or Discharge, whichever occurs first. Serum chemistry is collected at 24 (\pm 6 hours) and 48 hours (\pm 6 hours). All subjects must have a serum troponin drawn as part of the 24-hour (more frequently if clinically indicated) and 48-hour collections. Fluid balance (IV intake, output) data will be collected at 24 hours (\pm 6 hours) and 48 hours (\pm 6 hours). All subjects undergo a follow-up CT scan or brain MRI (including a minimum of diffusion-weighted imaging [DWI], gradient-echo [GRE], FLAIR, and intracranial MR angiography [MRA]) at 24 hours (\pm 6 hours) from the time of randomization. All subjects also undergo a clinical assessment of neurological and cardiological status at 24 hours (\pm 6 hours), 48 hours (\pm 6 hours), and 7 days (\pm 6 hours) or discharge, whichever comes first. This includes a NIHSS evaluation and standardized cardiac assessment. An EKG should be completed once during the 24-48 hour period. Both the baseline and 24-48h EKG must be reported centrally for review.

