7. CLINICAL MANAGEMENT OF ADVERSE EXPERIENCES

7.1 Complications of ALB Therapy

The major concern with ALB therapy is volume overload. ALB has oncotic properties and therefore draws sodium and water into the intravascular space. Subsequently ALB redistributes in total body water. Administration of ALB at higher doses in the Phase I Trial resulted in a 1.5 to 2 g/dL (15-20 g/L) increase in plasma albumin levels at 4 hours post-administration. The overall

incidence of clinical signs of CHF was approximately 13%, but in each case it was mild and the subjects responded to a maximum of 2 doses of furosemide.

Other potential cardiac complications of ALB therapy include atrial arrhythmias (e.g., atrial fibrillation/flutter) and possible myocardial ischemia. Volume infusion may promote atrial wall stress due to stretching, which could lead to atrial arrhythmias. A similar mechanism may occur, causing ischemia. Myocardial wall stress is associated with greater metabolic demand, which may not be available in a subject with coronary stenoses, as many stroke subjects may have. Further, the vast majority of stroke patients are chronic hypertensives, and such patients already tend to have reduced myocardial compliance.

Note that myocardial distress may occur, as shown by evidence of slightly elevated troponins, in up to 20% of ischemic stroke subjects, even without evidence of a true acute coronary syndrome. Thus, it is important to make a clear distinction between subjects who have troponin elevation due to an acute coronary syndrome and troponin elevation without acute coronary syndrome. The latter may be caused by the stroke and is presumed to arise by the same mechanism as seen in acute sub-arachnoid hemorrhage. Stroke may cause a catecholamine surge, possibly due to involvement of the insula, resulting in subendomyocardial damage.

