8. ADVERSE EVENTS REPORTING

8.1 Definition of Adverse Events

An *adverse event* is defined as any untoward event or complication that was not previously identified, or that occurs with greater frequency or severity than previously reported, which occurs during the protocol intervention or during the follow-up period, whether or not considered related to the protocol intervention. Abnormal laboratory findings considered by the reporting physician to be clinically significant are included as adverse events. The investigator, on the basis of his or her clinical judgment and the following definitions, determines the relationship of the adverse event to the protocol intervention as one of the following:

Definite: Causal relationship is certain (i.e., the temporal relationship between drug exposure and the adverse event onset/course is reasonable; there is a clinically compatible response to dechallenge; other causes have been eliminated; and the event must be definitive pharmacologically or phenomenologically, using a satisfactory rechallenge procedure if necessary).

Probable: High degree of certainty for causal relationship (i.e., the temporal relationship between drug exposure and the adverse event onset/course is reasonable; there is a clinically compatible response to dechallenge [rechallenge is not required]; and other causes have been eliminated or are unlikely).

Possible: Causal relationship is uncertain (i.e., the temporal relationship between drug exposure and the adverse event onset/course is reasonable or unknown; dechallenge/rechallenge information is either unknown or equivocal; and while other potential causes may or may not exist, a causal relationship to the study drug does not appear probable).

Unlikely: Not reasonably related, although a causal relationship cannot be ruled out (i.e., while the temporal relationship between drug exposure and the adverse event onset/course does not preclude causality, there is a clear alternate cause that is more likely to have caused the adverse event than the study drug).

Not related: No possible relationship (i.e., the temporal relationship between drug exposure and the adverse event onset/course is unreasonable or incompatible; or a causal relationship to study drug is implausible).

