Allergic reaction to ALB. Type I allergic reaction (anaphylaxis) manifesting as hives, laryngospasm, bronchospasm, hypotension (distributive shock).

Atrial fibrillation (AF). Supraventricular tachyarrhythmia characterized by uncoordinated atrial activation with consequent deterioration of atrial mechanical function. [122] Described on the EKG by the replacement of consistent P waves by rapid oscillations or fibrillatory waves that vary in size, shape, and timing, associated with an irregular, frequently rapid ventricular response when atrioventricular (AV) conduction is intact.[122] Any atrial fibrillation occurring post-treatment is considered an adverse event.

Atrial flutter. A more organized arrhythmia than AF and is characterized by a saw-tooth pattern of regular atrial activation called flutter (*f*) waves on the EKG, particularly visible in leads II, III, and aVF (inferior limb lead on a 12-lead EKG), without an isoelectric baseline between deflections.[122] Any atrial flutter occurring post-treatment shall be considered an adverse event.

Bowel pseudo-obstruction. Failure of peristalsis of the large bowel with associated dilatation. May result in sepsis and toxic megacolon.

Constipation. Hard, infrequent bowel motions. May be functionally defined as no bowel motion for 5 or more days.

Deep vein thrombosis (DVT) or pulmonary thrombo-embolism (PE). DVT and PE are spectrums of the same disease. A DVT is a thrombotic occlusion of a large vein in the leg, pelvis, abdomen, or arm. A PE is a thrombotic occlusion of a pulmonary artery, most often due to a venous embolus from a DVT.

Hemicraniectomy. Removal of a large ovoid region of the skull performed with an associated duroplasty to allow infarcted brain to swell without causing rostral-caudal deterioration and death.

Sudden vascular death. Deaths are categorized as sudden cardiovascular if they are unexpected, rapidly follow symptoms, and are attributable to a cardiovascular or unexplained cause. [122]

Pulmonary hypertension. (A) Measured (e.g., Swann-Ganz catheter) or estimated (echocardiography) right ventricular end-diastolic pressure greater than 10 mm Hg; or (B) Measured or estimated using echocardiography, a peak right ventricular systolic pressure > 25mm Hg.

Renal failure. Renal failure shall be defined as renal dysfunction requiring artificial renal replacement therapy (hemodialysis or peritoneal dialysis).

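### Sections 8.2 and 8.8 count post-treatment atrial fibrillation without reference to baseline rhythm, which fits poorly with 8.1 and can dilute the comparison between arms

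*Protocol*

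**What the plan says.** - **Event definition (Protocol 8.2).** "Any atrial fibrillation occurring post-treatment is considered an adverse event". The flutter entry reads the same way: "Any atrial flutter occurring post-treatment shall be considered an adverse event".
- **Monitored item (Protocol 8.8).** The events followed by treatment group throughout the study include "Atrial fibrillation within 48 (\pm 6) hours of randomization". Nothing restricts this to new AF.
- **Eligibility (Protocol 4.2, criterion 9).** Acute arrhythmia is excluded only when it comes with "hemodynamic instability on admission (systolic blood pressure < 100 mmHg"). Criterion 10 adds tachycardia only if it is attributable to heart failure.
- **Why the event is watched (Protocol 7.1).** "Volume infusion may promote atrial wall stress due to stretching, which could lead to atrial arrhythmias".
- **General definition (Protocol 8.1).** An adverse event is "any untoward event or complication that was not previously identified, or that occurs with greater frequency or severity than previously reported".
- **Data available (Protocol 6.1 and 6.2.2).** Medical history and an EKG are collected at baseline. "Both the baseline and 24-48h EKG must be reported centrally for review".
- **Formal safety testing (Protocol 10.2.3 and 10.7.2).** Only 30-day death is evaluated statistically and has a stopping guideline.

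**The concern.** The harm that 7.1 describes is arrhythmia brought on by volume infusion. AF that was present before the infusion says nothing about that harm. Yet a hemodynamically stable patient who arrives in AF can be randomized, will probably still be in AF over the next two days, and meets the literal wording of 8.2 and 8.8 in either arm.

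Other entries in 8.2 do refer to baseline or to new findings: the Q-wave criterion for infarction, the creatinine rise, treatment-emergent hypertension, neurological deterioration on the NIHSS, and recurrent stroke. The AF and flutter entries do not.

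At stake is how readable one cardiac harm signal is for the DSMB. The 48-hour count could mix new, recurrent and long-standing AF in unknown proportions, and those proportions could differ between sites.

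**Working it through.** **Step 1: set the sections side by side.**

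| Situation | Under 8.2/8.8 read literally | Under 8.1 |
|---|---|---|
| Known permanent AF, unchanged | Event | Not an event |
| AF first seen on the baseline EKG for this stroke, persisting | Event | Unclear: 8.1 does not say identified when, or by whom |
| Known paroxysmal AF, new episode after treatment | Event | Depends on whether frequency or severity is judged greater |
| No prior AF, onset after treatment | Event | Event |

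The two definitions clearly agree only on the last row. The synopsis plans about 100 centers, so different coding of the first three rows is a real possibility.

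**Step 2: the size if the literal reading is applied.** The protocol states no AF prevalence, AF rate, or alpha for AF, so there is no figure to reproduce.

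Input from the protocol: about 1,100 subjects randomized 1:1, so about 550 per arm.

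Assumptions:
- p, the share in AF at baseline, from 5% to 25%;
- r, the new-onset rate in the rest, 3% on saline and 8% on albumin;
- every subject with baseline AF is counted;
- two-sided 5% test, normal approximation for two proportions.

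Formulas:
- counted rate = p + (1 − p) × r
- counted difference = (1 − p) × (8% − 3%)
- n per arm for new-onset AF = 550 × (1 − p)

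Example at p = 20%:
- saline: 0.20 + 0.80 × 0.03 = 22.4%
- albumin: 0.20 + 0.80 × 0.08 = 26.4%
- risk ratio: 26.4 / 22.4 = 1.18
- difference: 4.0 points

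| p | Saline, counted | Albumin, counted | Risk ratio, any AF | Difference (points) | Power, any AF | Power, new-onset only |
|---|---|---|---|---|---|---|
| 5% | 7.85% | 12.6% | 1.61 | 4.75 | 74% | 94% |
| 10% | 12.7% | 17.2% | 1.35 | 4.5 | 55% | 93% |
| 20% | 22.4% | 26.4% | 1.18 | 4.0 | 34% | 90% |
| 25% | 27.25% | 31.0% | 1.14 | 3.75 | 28% | 88% |

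Among subjects free of AF at baseline, the risk ratio is 8/3 = 2.67 throughout and the difference is 5.0 points. The power columns only index sensitivity, because the protocol plans no such test.

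**Step 3: other assumed rates.**
- 5% vs 10% (true ratio 2.0): the counted ratio is 1.49 at p = 5% and 1.17 at p = 20%. Power is 68% and 33%, against 87% and 80% for new-onset AF only.
- 3% vs 6% (true ratio 2.0): the counted ratio is 1.36 at p = 5% and 1.11 at p = 20%. Power is 37% and 15%, against 65% and 57%.

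The direction is the same in every case. The size depends wholly on p and the new-onset rates.

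**The case against.** The strongest reply is that 8.1 governs. The entries in 8.2 are selected adverse events, so the general condition carries over and known, unchanged AF is not an event. The phrase about occurring after treatment can also mean onset after treatment, and 8.4 requires an onset date for each adverse event, which for permanent AF would precede randomization. This is a fair reading, and it means that literal counting of all baseline AF is not certain. It does not settle the matter. A site may reasonably let a specific rule about *any* AF override a general clause, and 8.1 leaves AF first found at presentation and recurrent paroxysmal AF open.

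Three further points stand:
- AF has no formal test or boundary, and the DSMB may ask for more data and weigh everything before it.
- Baseline and 24-48 hour EKGs are read centrally, so new AF can be partly separated later. However, 6.2.2 asks for only one EKG in that window, and it can miss a transient episode that a site reported.
- Broad capture at sites, sorted afterwards, is a defensible way to avoid under-reporting. The fix below keeps that capture and changes only what is counted as the monitored event.

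A reader might infer that the monitored rate is swamped by pre-existing AF and that an albumin effect would be hidden. The documents do not support this. They give no prevalence or event rate, 8.1 may keep much of the pre-existing AF out of the count, and the absolute difference between arms falls only by the factor (1 − p).

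**Conclusion.** The point holds as a defect of definition with a limited, conditional effect. Sections 8.2 and 8.8 carry no baseline-rhythm condition, stable AF is eligible, and 8.1 points the other way, so the sections need to be reconciled on either reading.

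If the literal wording is followed, pre-existing AF adds equally to both arms in expectation. The risk ratio moves toward 1 and sensitivity to an albumin-induced excess falls, while most of the absolute excess remains. Under the assumed 3% vs 8%, the ratio of 2.67 appears as about 1.6 at 5% baseline AF and about 1.2 at 20%, with differences of 4.75 and 4.0 points instead of 5.0. These figures rest on assumed rates and on every case of baseline AF being recorded, so they are upper illustrations of the dilution at each prevalence.

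The wording problem is certain and its size is not. It is worth correcting because the repair is cheap and 7.1 names the risk.

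**What to change.** Reconcile 8.2 and 8.8 with 8.1:

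1. Define the monitored event as new-onset AF or flutter: documented after the start of study drug in a subject with neither on the centrally read baseline EKG nor in the medical history. The 8.8 item now names AF only, so this also brings flutter in, as 7.1 suggests.
2. Use subjects free of AF and flutter at baseline as the denominator.
3. Report recurrence or worsening of known AF or flutter by arm on a separate line, so that events of greater frequency or severity under 8.1 are still seen.

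The cost is a wording change in two sections, matching guidance for sites, and one flag derived from the baseline EKG and history already collected. The small downside is that subjects with baseline AF or flutter leave the main denominator. In the illustration this lowers the number per arm from 550 to 440 at 20% prevalence (550 × 0.80).
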